3.9.2. Clinical Laboratory Parameters

Laboratory parameters will be presented in conventional (ie, US) units. Only scheduled laboratory parameters will be included in the summaries, unless specified otherwise. All laboratory data, including those collected at unscheduled visits, will be included in the listings.

Laboratory results including baseline and change from baseline during the treatment period for chemistry and hematology parameters will be summarized by visit.

Clinical laboratory test values, scheduled or unscheduled, will be considered potentially clinically significant (PCS) if they meet PCS criteria listed in [Table 3](#). The number and percentage of subjects who have postbaseline PCS clinical laboratory values will be summarized. The percentages will be calculated based on the number of subjects with non-PCS baseline value and have at least one postbaseline assessment. All PCS values including baseline PCS values will be included in supportive listings.

For selected metabolic parameters (fasting total cholesterol, fasting high density lipoprotein[HDL], fasting low density lipoprotein[LDL], fasting triglycerides, fasting glucose, and hemoglobin A1c[HbA1c]), an analysis of sustained PCS values will also be conducted. The percentage of subjects with sustained PCS values through the treatment period will be summarized. The denominator is all subjects with non-PCS at baseline and at least two postbaseline assessments, and the numerator is the number of subjects who met PCS criteria at the last 2 assessments within the treatment period.

Shift tables for selected fasting metabolic parameters (total cholesterol, LDL, HDL, triglycerides, glucose and HbA1c) and liver function tests will be presented. The criteria are summarized in [Table 4](#), [Table 5](#) and [Table 6](#).

Table 3: Criteria of Potentially Clinically Significant (PCS) Abnormality for Selected Analytes

Parameter	Criteria
Chemistry	
Albumin	<2.5 g/dL
Alkaline Phosphatase (U/L)	$\geq 3 \times \text{ULN}$
Alanine Aminotransferase (U/L)	$\geq 3 \times \text{ULN}$
Aspartate Aminotransferase (U/L)	$\geq 3 \times \text{ULN}$
Bilirubin, Total	$\geq 2.0 \text{ mg/dL}$
Blood Urea Nitrogen	>30 mg/dL
Cholesterol, Random	>300 mg/dL
Cholesterol, Fasting ^a	$\geq 240 \text{ mg/dL}$
Cholesterol, Fasting	Increase $\geq 40 \text{ mg/dL}$
Cholesterol, HDL Fasting	<40 mg/dL
Cholesterol, HDL Fasting	Decrease $\geq 20 \text{ mg/dL}$
Cholesterol, LDL Fasting	$\geq 160 \text{ mg/dL}$
Cholesterol, LDL Fasting	Increase $\geq 30 \text{ mg/dL}$
Creatine Kinase (U/L)	$\geq 3 \times \text{ULN}$
Creatinine	$\geq 2.0 \text{ mg/dL}$
Glucose, Random	<50 mg/dL or $\geq 200 \text{ mg/dL}$
Glucose, Fasting	<50 mg/dL or $\geq 126 \text{ mg/dL}$
Glucose, Fasting	Increase $\geq 10 \text{ mg/dL}$
HbA1c	$\geq 5.7\%$
Potassium	<3 mmol/L or >5.5 mmol/L
Lactate Dehydrogenase (U/L)	$> 3 \times \text{ULN}$
Prolactin (Female)	>30 ng/mL
Prolactin (Male)	>20 ng/mL
Sodium	<130 mmol/L or >150 mmol/L

Table 3: Criteria of Potentially Clinically Significant (PCS) Abnormality for Selected Analytes (Continued)

Triglycerides, Fasting	≥200 mg/dL
Triglycerides, Fasting	Increase ≥50 mg/dL
Hematology	
Eosinophils	>1.0 × 10 ³ /μL
Hematocrit (Female)	≤32%
Hematocrit (Male)	≤37%
Neutrophils, Absolute	<1.5 × 10 ³ /μL
Platelets	<75.0 × 10 ³ cells/μL or ≥ 700.0 × 10 ³ cells/μL
Leukocytes	≤ 2.8 × 10 ³ /μL or ≥ 16.0 × 10 ³ /μL

^a reported fasting.

Table 4: Shifts Categories from Baseline to Any Postbaseline for Selected Lipid Parameters

Total Cholesterol (fasting) mg/dL
Normal (<200) to High (≥240)
Borderline (≥200 and < 240) to High (≥240)
Normal (<200) to Borderline (≥200 and <240)
LDL Cholesterol (fasting) mg/dL
Normal (<100) to High (≥160)
Borderline (≥100 and <160) to High (≥160)
Normal (<100) to Borderline (≥100 and <160)
HDL Cholesterol (fasting) mg/dL
Normal (≥40) to Low (<40)
Triglycerides (fasting) mg/dL
Normal (<150) to High (≥200)
Borderline (≥150 and <200) to High (≥200)
Normal (<150) to Borderline (≥150 and <200)

Table 5: Shift Categories from Baseline to Any Postbaseline in Glucose and HbA1c

Glucose (fasting) mg/dL
Normal (<100) to Impaired (≥ 100 and <126)
Normal (<100) to High (≥ 126)
Impaired (≥ 100 and <126) to High (≥ 126)
HbA1c %
Normal (<5.7%) to Borderline ($\geq 5.7\%$ and <6.5%)
Borderline ($\geq 5.7\%$ and <6.5%) to High ($\geq 6.5\%$)
Normal (<5.7%) to High ($\geq 6.5\%$)

Table 6: Shift Categories from Baseline to Any Postbaseline in Liver Function Test

Alanine Aminotransferase (ALT) (U/L)
Shift from Normal to ≥ 3 x ULN
Shift from Normal to ≥ 5 x ULN
Shift from Normal to ≥ 10 x ULN
Aspartate Aminotransferase (AST) (U/L)
Shift from Normal to ≥ 3 x ULN
Shift from Normal to ≥ 5 x ULN
Shift from Normal to ≥ 10 x ULN
Bilirubin, Total (mg/dL)
Shift from Normal to >1 x ULN
Shift from Normal to ≥ 2 x ULN

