8.3.4. Concomitant Medication Review

At the time points specified in [Table 3](#) subjects will be asked about the medications they have taken since their last visit, including prescription and nonprescription medications, vitamins, and supplements.

The investigator will record the following data on all medications used by the subject: name, dose, regimen, route of administration, start and stop dates, and the indication for use.

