8.4.2. Prohibited Medications

The prohibited medications include the following:

- Monoamine oxidase inhibitors (eg, phenelzine, tranylcypromine, selegiline, or moclobemide)
- Long-acting formulations of any antipsychotic agent
- Use of antipsychotic sleep aids (eg, Seroquel) is prohibited. However, use of benzodiazepines to treat some symptoms is permissible
- In general, the use of psychotropic medications other than study drug is prohibited with the exception of the following (these medications should only be administered after all assessments have been completed for that visit):
 - Beta-blockers (eg, propranolol or pinodolol), antihistamines, and anticholinergics may be used for treatment-emergent akathisia
 - Anticholinergics may be used for extrapyramidal symptoms
- Chantix[®] (varenicline) is not permitted. However, nicotine replacement therapy including nicotine replacement patch and oral nicotine gum is permitted
- All prescription or over-the-counter (OTC) agents taken for the purpose of weight reduction
- Systemic steroids administered by oral, intravenous, or intramuscular route
- Topiramate (Topamax[®]) and combination products containing topiramate; Calcitonin (eg, Miacalcin[®])
- Diabetes treatments and hypoglycemic agents including Metformin and Insulin

Medications that are contraindicated with olanzapine use or exhibit drug-interaction potential with olanzapine are prohibited (see [ALKS 3831 Investigator Brochure](#)).

Use of moderate to strong inducers or inhibitors of cytochrome P450 (CYP) 3A4 (prescription medications, OTC medications, or dietary supplements) was prohibited in the antecedent study ([ALK3831-A303](#)) and will be prohibited in this study from Visit 1 through follow-up. Refer to

[Appendix A](#) for a list of CYP3A4 inhibitors and inducers ([Food and Drug Administration 2016](#); [University of Washington: School of Pharmacy 2017a](#); [University of Washington: School of Pharmacy 2017b](#)).

The CRO medical monitor should be consulted for any questions about use of any psychotropic medications during a subject's participation in this study.

Use of opioid antagonists, including naltrexone (any formulations) and naloxone throughout the study period is prohibited. Note: during the study period, opioid agonists should be avoided as they may be rendered ineffective by samidorphan.

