14.4. Safety and Tolerability Analyses

Incidence of AEs will be analyzed as a safety endpoint. Reported adverse event terms will be coded using the Medical Dictionary for Regulatory Activities (MedDRA) and summarized by system organ class and preferred term categories.

SAEs and AEs contributing to study discontinuation will also be summarized.

Observed values and change from baseline in weight, BMI, waist circumference, laboratory parameters, vital signs, and ECG parameters will be summarized by study visit.

The number and percentage of subjects who have met potentially clinically significant (PCS) criteria at any post-baseline visit will be summarized for laboratory, vital signs, weight, and ECG parameters. Supporting listings will be provided.

The number and percentage of subjects with shifts in laboratory and EPS parameters (AIMS, BARS, and SAS) will be summarized. Supporting listings will be provided.

The number and percentage of subjects with C-SSRS assessments of suicidal ideation and behavior will be summarized.

Prior and concomitant medication use will be summarized by World Health Organization (WHO) Drug Dictionary Anatomical Therapeutic Class (ATC) code.

Listings will be provided for all safety endpoints.

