3.6. Prior and Concomitant Medication

Prior medications will be defined as medications taken prior to the first dose of study drug in ALK3831-A304 study. Concomitant medications will be defined as medications taken on or after the first dose of study drug in ALK3831-A304 study. All medications will be coded using the World Health Organization WHO-DD Enhanced + Herbal (version: March 2016) or higher.

Concomitant medications taken during the treatment period will be summarized by the preferred drug name. All reported medications (including those initiated after the last dose of study medication) will be included in the listing. For the summary table, if a subject has taken a concomitant medication more than once, the subject will be counted only once for that medication.

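### The sustained-PCS lipid rule in SAP 3.9.2 makes no allowance for lipid-lowering drugs, so a rise that is treated can be scored as not sustained

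*SAP*

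**What the plan says.** SAP 3.9.2 states that for six metabolic parameters (fasting total cholesterol, HDL, LDL, triglycerides and glucose, plus HbA1c) "an analysis of sustained PCS values will also be conducted". Everyone who was not PCS when the study began and who has two or more later values enters the denominator. The rule for counting a case is: "the numerator is the number of subjects who met PCS criteria at the last 2 assessments within the treatment period". SAP section 7 bases every summary table on observed data. No SAP section says how to treat lipid values obtained after a lipid-lowering drug has been started.

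Among metabolic drugs, protocol 8.4.2 prohibits "Diabetes treatments and hypoglycemic agents including Metformin and Insulin" and "All prescription or over-the-counter (OTC) agents taken for the purpose of weight reduction". It lists no lipid-lowering class. Protocol 8.4.3 deals with extrapyramidal symptoms, akathisia, insomnia, agitation and anxiety only. The partial CYP3A4 list in Appendix A names no statin, fibrate or ezetimibe.

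On medication reporting, protocol 14.4 says: "Prior and concomitant medication use will be summarized by World Health Organization (WHO) Drug Dictionary Anatomical Therapeutic Class (ATC) code". SAP 3.6 says: "Concomitant medications taken during the treatment period will be summarized by the preferred drug name". SAP section 5, which records departures from the protocol, lists only the CGI-S shift analysis. For each drug, protocol 8.3.4 collects the name and dosing details together with "start and stop dates, and the indication for use".

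**The concern.** The sustained-PCS analysis has one job: to separate a lipid abnormality that persisted from one that came and went. A rise that a physician chose to treat is hard to regard as transient. Under the last-two rule, however, successful treatment places it with the transient ones.

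The gap is specific to lipids. The protocol closes the same route for glucose and HbA1c by prohibiting diabetes treatments, so only protocol deviations could open it. The lipids have no such protection in the protocol and none in the SAP.

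Treatment during the study is foreseeable. The study is open-label and treatment lasts 52 weeks. Under protocol 13.1 investigators must judge each out-of-range laboratory value, and those judged clinically significant become adverse events. Protocol 13.4 leaves therapeutic measures to the investigator.

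Long-term safety is the primary objective, and protocol 5.1 presents the product as intended to lessen the metabolic burden of olanzapine. A sustained-lipid percentage that treatment can lower, shown without the number treated, is hard to interpret. By-visit lipid means are affected in the same direction.

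**Working it through.** **1. Inputs.** The plan has no figure to reproduce: there is no sample size calculation, expected PCS rate or rate of lipid-lowering drug use. The rule comes from SAP 3.9.2. Scheduled postbaseline laboratory draws (protocol Table 3) are read here as Weeks 4, 12, 24, 36 and 52. The planned size of about 540 (SAP section 2) serves only as an upper bound for the denominator, which excludes subjects who are PCS at baseline or have fewer than two postbaseline values.

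**2. The rule applied to possible histories.**

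| History (Weeks 4, 12, 24, 36, 52) | Any postbaseline PCS | Sustained under SAP |
|---|---|---|
| Untreated: normal, PCS, PCS, PCS, PCS | yes | yes |
| Treated after Week 24: PCS, PCS, PCS, normal, normal | yes | no |
| Treated after Week 36: PCS, PCS, PCS, PCS, normal | yes | no |
| Treated after Week 24, not held: normal, PCS, PCS, normal, PCS | yes | no |
| Treated, inadequate response: normal, PCS, PCS, PCS, PCS | yes | yes |

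Five draws give 2^5 = 32 possible patterns. Of these, 19 contain two consecutive PCS values and 8 satisfy the last-two rule, so 19 − 8 = 11 are classed as not sustained despite two consecutive PCS values. These are counts of patterns, not frequencies. They show how the rule behaves, not how often it matters.

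A single value below the limit among the last two is enough to remove a subject. A drug started after the Week 36 draw therefore has the same effect if the Week 52 value falls below the limit.

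**3. Illustrative size.** Let
- s = sustained rate in the absence of lipid treatment,
- t = share of those subjects who start a lipid-lowering drug,
- c = share of those treated who have at least one of the last two values below the limit.

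Reported rate = s × (1 − t × c). Subjects missed = 540 × s × t × c, as an upper bound. All three inputs are assumptions.

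| s | t | c | Reported rate | Missed, of 540 |
|---|---|---|---|---|
| 10% | 10% | 50% | 0.10 × (1 − 0.05) = 9.5% | 2.7, about 3 |
| 20% | 30% | 80% | 0.20 × (1 − 0.24) = 15.2% | 25.9, about 26 |
| 30% | 50% | 100% | 0.30 × (1 − 0.50) = 15.0% | 81 |

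The relative understatement is t × c, which runs from 0.10 × 0.50 = 5% to 0.50 × 1.00 = 50% over these ranges.

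**4. Can a reader gauge the effect from the planned tables?** Rows by drug name cannot be summed to subjects, because one subject may appear under several drugs. SAP 3.6 defines a concomitant drug as one taken on or after first dose, so subjects continuing a drug and subjects starting one share a row. The listings hold the information, but no planned table gives the number who newly started any lipid-lowering drug.

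**The case against.** The strongest reply is that the rise is not lost. SAP 3.9.2 tabulates any postbaseline PCS value, scheduled or unscheduled, and lists all PCS values. Table 4 gives shifts to any postbaseline value. Values judged clinically significant also become adverse events. On the SAP's own definition, an abnormality gone by the end is not sustained, and summarising observed values whatever the co-medication is a recognised descriptive choice. All of this stands. It confines the problem to the sustained row and the by-visit means. It does not dispose of it, because none of the other tables shows whether the abnormality persisted or resolved only under treatment.

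A reader might infer four stronger things that the documents do not support.
- *That lipid-lowering drugs are expressly permitted.* They are not prohibited as a class, and no section expressly allows them. Drugs with interaction potential remain subject to protocol 7.2 and 8.4.2.
- *That the SAP conceals their use.* Each drug would appear by name and every medication is listed. What is missing is the class total and the number of new starters.
- *That the rule biases a comparison in favour of ALKS 3831.* Every subject receives ALKS 3831, there is no concurrent comparator, and SAP 3.8.4 treats multiplicity as not applicable. The effect is a lower absolute percentage. Whether the two treatment sequences differ in drug starts is unknown.
- *That any treated case disappears.* A treated subject who is still PCS at both last assessments is counted.

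**Conclusion.** The point holds as a consequence of the text. For total cholesterol, LDL and triglycerides, effective treatment can only remove subjects from the sustained-PCS numerator while leaving the denominator unchanged, so the direction is known: the reported percentage can be too low as a measure of lipid abnormality that would have persisted untreated. The size is not known. The 5% to 50% relative range rests entirely on assumed values of s, t and c. Only rises above the A304 baseline, at the end of the 24-week antecedent study, are exposed, because subjects already PCS at that baseline are outside the denominator.

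HDL is left out because its PCS criterion is a low value or a decrease, to which the argument does not carry over directly.

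The difference between protocol 14.4 and SAP 3.6 on ATC coding is a separate inconsistency and stands whatever the treatment rate. It matters here because the ATC summary is the natural place to see how much lipid-lowering treatment occurred.

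This is a worthwhile, moderate improvement to a descriptive safety table. It is not a flaw in the primary evidence on whether lipids rose.

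**What to change.** **SAP 3.9.2.** Keep the stated sustained-PCS row. Beside it, for total cholesterol, LDL and triglycerides, add a supplementary row with the same denominator, by treatment sequence and overall: PCS at the last 2 assessments, or a postbaseline PCS value followed by on-treatment start of a lipid-lowering drug. Show the two components separately, the second limited to subjects not already in the first. A single PCS value followed by treatment is then visible as such and is not passed off as persistence. SAP 6.2 moves partial medication start dates to the earliest possible date, so footnote the number of starts whose order relative to the PCS value depends on that convention.

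**SAP 3.6.** Restore the ATC-code summary required by protocol 14.4, or list the change in SAP section 5. In either case show, by treatment sequence, the number of subjects newly starting any lipid-lowering drug after first dose.

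**By-visit lipid means.** Keep them as observed, with a footnote giving the number of subjects on lipid-lowering therapy. Setting aside values after the start of treatment is not advised. It would selectively drop subjects with high lipids from later visits, an informative exclusion that could itself make the means look better.

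**Cost.** SAP wording, one drug-class flag derived from medication data already collected and coded, and a few table rows. The percentage in the supplementary row may be less favourable than the stated one. Nothing changes in study conduct or in which medications are allowed.

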8.2. Schedule of Visits and Assessments

The schedule of visits and assessments is shown in [Table 3](#).

A visit window of ± 2 days is allowed throughout the treatment period and during the follow-up period. For a missed visit, the site must contact the subject to reschedule.

Premature discontinuation procedures are provided in [Section 7.3](#). Subjects who discontinue study drug but are willing to come in for further assessments will be asked to complete the ET visit (same assessments as Visit 27, [Table 3](#)) followed by 2 safety follow-up visits 2 and 4 weeks after the ET visit (same assessments as Visits 28 and 29 in [Table 3](#)). They will then be asked to return to the study center for monthly visits according to the schedule outlined in [Table 3](#), to collect the following information: weight assessments, any new antipsychotic medications the subject is taking, and adverse events.

Table 3: Schedule of Visits and Assessments

Visit ^a	Treatment Period																										Follow-Up Period			
	1 ^b	2	3	4	5	6	7	8	9	10	11	12	13	14	15	16	17	18	19	20	21	22	23	24	25	26	27/ ET	28 ^c	29	
Study week	-	2	4	6	8	10	12	14	16	18	20	22	24	26	28	30	32	34	36	38	40	42	44	46	48	50	52	54	56	
Informed Consent	X																													
Eligibility Criteria	X																													
Pregnancy Testing ^d	X						X					X							X											
Urine Drug Screen ^e	X						X					X							X								X			
Weight ^f		X	X	X	X		X		X		X		X		X		X		X		X		X		X		X		X	
Waist Circumference		X	X	X	X		X		X		X		X		X		X		X		X		X		X		X		X	
Vital Signs ^g		X	X	X	X		X		X		X		X		X		X		X		X		X		X		X		X	
Laboratory Samples ^h			X				X					X							X								X			
ECG			X				X					X							X								X			
Physical Exam			X				X					X							X								X			
PANSS ⁱ		X	X		X		X					X							X								X			
CGI-S		X	X		X		X		X		X		X		X		X		X		X		X		X		X		X	
AE ^j		X	X	X	X	X	X	X	X	X	X	X	X	X	X	X	X	X	X	X	X	X	X	X	X	X	X	X	X	X
ConMed Review ^j		X	X	X	X	X	X	X	X	X	X	X	X	X	X	X	X	X	X	X	X	X	X	X	X	X	X	X	X	X
C-SSRS ^k		X	X	X	X	X	X	X	X	X	X	X	X	X	X	X	X	X	X	X	X	X	X	X	X	X	X	X	X	X

Table 3: Schedule of Visits and Assessments (Continued)

Visit ^a	Treatment Period																											Follow-Up Period	
	1 ^b	2	3	4	5	6	7	8	9	10	11	12	13	14	15	16	17	18	19	20	21	22	23	24	25	26	27/ET	28 ^c	29
Study week	-	2	4	6	8	10	12	14	16	18	20	22	24	26	28	30	32	34	36	38	40	42	44	46	48	50	52	54	56
Abnormal Movement Scales ^l			X				X						X						X								X		
IWQOL			X				X						X						X								X		

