EQ-5D			X				X						X						X								X		
Cigarette Use			X				X						X						X								X		
Emergency Treatment Card ^m	X	X	X	X	X	X	X	X	X	X	X	X	X	X	X	X	X	X	X	X	X	X	X	X	X	X	X	X	X
Study Drug Dispensation	X	X	X	X	X	X	X	X	X	X	X	X	X	X	X	X	X	X	X	X	X	X	X	X	X	X	X	X	X
Study Drug Adherence Review		X	X	X	X	X	X	X	X	X	X	X	X	X	X	X	X	X	X	X	X	X	X	X	X	X	X	X	X

Abbreviations: AE=adverse event; CGI-S=Clinical Global Impression-Severity; ConMed=concomitant medications; C-SSRS=Columbia-Suicide Severity Rating Scale; EOT=end of treatment; ECG=electrocardiogram; EQ-5D=EuroQol five dimensions questionnaire; IWQOL=impact of weight on quality of life; PANSS=Positive and negative syndrome scale

^a A visit window of ±2 days is allowed throughout the treatment period and during the follow-up period.

^b Visit 1 must occur within 7 days of the end of treatment visit (Visit 17) of the antecedent study, ALK3831-A303, and may occur on the same day. Assessments from ALK3831-A303 Visit 17 will constitute the baseline/screening assessments for this extension study.

^c Follow-up visits (Visits 28 and 29) are not required for subjects who enroll in ALK3831-A308

^d Urine pregnancy test at Visit 1 and at all subsequent specified visits.

^e Urine drug screen via dipstick prior to study drug dispensation at Visit 1, Visit 7, Visit 13, Visit 19 and Visit 27. Urine drug screen tests include, tests for opiates (including codeine, hydrocodone, hydromorphone, methadone, morphine, oxycodone, and oxymorphone) and drugs of abuse (including amphetamine/methamphetamine, phencyclidine [PCP], and cocaine)

^f Subjects that prematurely discontinue study drug will be asked to come in for monthly follow-up assessments of weight, adverse events and any new antipsychotic medications following an early termination (ET) visit and two safety follow-up visits.

-
- ^g Vital signs include orthostatic blood pressure and heart rate, respiratory rate, and oral body temperature. Orthostatic blood pressure and pulse rate will be taken after the subject has been supine for 5 minutes and once again after the subject has stood for 2 minutes.
- ^h Subjects must fast (no food or drink except water) for at least 8 hours before lab draws. Lab draws are to be conducted in the morning for all specified visits.
- ⁱ PANSS should be administered before other psychiatric assessments at each specified study visit.

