3.9.3. Vital Signs, Body Weight, and ECG

3.9.3.1. Vital Signs

Descriptive statistics for vital signs and changes from baseline values at each scheduled time point will be presented.

Vital sign values will be considered PCS if they meet both the observed-value criteria and the change-from-baseline criteria listed in [Table 7](#). The number and percentage of subjects with PCS postbaseline values will be tabulated. The percentages will be calculated based on the number of subjects with non-PCS baseline values and at least one postbaseline assessment. The numerator

will be the number of subjects with non-PCS baseline values and at least one postbaseline PCS value. A supportive listing of subjects with PCS postbaseline values will be provided.

All vital signs will be presented in the subject data listing.

Orthostatic hypotension (20/10 mmHg) is defined as a fall in systolic blood pressure of at least 20 mmHg and a fall in the diastolic blood pressure of at least 10 mmHg upon standing from supine. Orthostatic hypotension (30 mmHg) is defined as a fall in systolic blood pressure of at least 30 mmHg upon standing from supine.

Orthostatic tachycardia is defined as a heart rate increase of 30 beats per minute (bpm) or more upon standing from supine, or over 120 bpm upon standing.

The number and percentage of subjects with orthostatic hypotension or orthostatic tachycardia occurring at any postbaseline visit will be summarized.

Table 7: Criteria for Potentially Clinically Significant (PCS) Blood Pressure or Pulse Rate

Parameter	Criteria
Supine Systolic Blood Pressure	≤ 90 and decrease ≥ 20 mm Hg ≥ 180 and increase ≥ 20 mm Hg
Supine Diastolic Blood Pressure	≤ 50 and decrease ≥ 15 mm Hg ≥ 105 and increase ≥ 15 mm Hg
Supine Heart Rate	≤ 50 and decrease ≥ 15 bpm ≥ 120 and increase ≥ 15 bpm

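### The adjacent-category rows of the lipid, glucose and HbA1c shift tables count only worsening at any of five draws, and the Borderline lipid and Impaired glucose rows have neither a confirmed nor a two-way counterpart

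*SAP*

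**What the plan says.** SAP section 3.9.2 states: "Shift tables for selected fasting metabolic parameters (total cholesterol, LDL, HDL, triglycerides, glucose and HbA1c) and liver function tests will be presented". The lipid table is titled "Shifts Categories from Baseline to Any Postbaseline for Selected Lipid Parameters", and the glycaemic one is "Table 5: Shift Categories from Baseline to Any Postbaseline in Glucose and HbA1c".

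- **Rows.** Table 4 has 10 rows and Table 5 has 6, and every row is a worsening. Eleven move to the adjacent category, for example "Normal (<100) to Impaired (≥ 100 and <126" mg/dL. Five skip a category, for example "Normal (<200) to High (≥240" mg/dL.
- **Baseline.** One value, the last non-missing one before first dose in this study (SAP 3.1).
- **Draws.** Only scheduled values enter the summaries unless otherwise specified (SAP 3.9.2). The laboratory row of protocol Table 3 has five marks, read here as Visits 3, 7, 13, 19 and 27 (Weeks 4, 12, 24, 36 and 52). The mid-study column is hard to read in the extracted table. The urine drug screen has a mark in that same column, and its footnote lists "Visit 1, Visit 7, Visit 13, Visit 19 and Visit 27".
- **Related analyses in 3.9.2.** By-visit change from baseline; PCS criteria (Table 3) that include changes for lipids and fasting glucose; and a sustained-PCS analysis for the same six analytes, requiring PCS at the last two on-treatment assessments.
- **Denominator.** Stated for PCS, not for the shift tables.
- **Control.** Both treatment sequences receive ALKS 3831 in this study (SAP 3.1).

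**The concern.** In an adjacent-category row the baseline limit and the event limit are the same number, so glucose of 99 at baseline and 100 mg/dL at one later draw is a worsening. Taking the worst of five draws raises the count further, and falls across the same line have no cell. With no concurrent control, the table cannot tell visit-to-visit variation from a drug effect.

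The plan is more balanced elsewhere. The CGI-S shift table (SAP Table 2) has improvement and worsening rows. The weight PCS criteria (SAP Table 8) count decreases and increases. For vital signs, "Vital sign values will be considered PCS if they meet both the observed-value criteria and the change-from-baseline criteria". Protocol section 14.4 promises laboratory shifts without limiting their direction.

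Long-term safety is the primary objective, and reduced metabolic harm is part of the product's rationale (protocol 5.1). Large worsening percentages could be read as caused by the drug. Any improvement in the OLZ/ALKS 3831 sequence after leaving olanzapine alone would not appear in these tables.

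**Working it through.** The documents state no shift rate and no variability figure, so there is no planned figure to reproduce. The check asks what the tables would show if nothing changed.

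**1. Classify the rows.** Total cholesterol, LDL, triglycerides, glucose and HbA1c have three rows each and HDL has one: 5 × 3 + 1 = 16. Five are Normal to High, leaving 11 adjacent. The Normal-to-High rows imply a minimum rise:

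- total cholesterol: 240 − 200, so more than 40 mg/dL
- LDL: 160 − 100, more than 60 mg/dL
- triglycerides: 200 − 150, more than 50 mg/dL
- glucose: 126 − 100, more than 26 mg/dL
- HbA1c: 6.5 − 5.7, more than 0.8 points

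**2. Compare the cut-offs with Table 3.** Its level criteria match the shift tables at total cholesterol 240, LDL 160, triglycerides 200, glucose 126, HDL 40 and HbA1c 5.7%. None sits at total cholesterol 200, LDL 100, triglycerides 150 or glucose 100.

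**3. Model.** Each subject has a constant true level plus independent noise at one baseline and five later draws. The rate is P(any of 5 values at or beyond the cut-off, given baseline on the normal side), simulated with 400,000 subjects per setting.

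A hand calculation shows the mechanism. With true glucose 97 and within-subject SD 5, the chance of reaching 100 at one draw is 1 − Φ(0.6) = 0.274. At any of five it is 1 − 0.726⁵ = 0.80.

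**4. Results, main assumptions (none from the documents).**

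| Analyte | Mean, between-subject SD | Within-subject SD or CV | Normal to next category or worse |
|---|---|---|---|
| Glucose | 90, 7 | 3 to 6 | 11-28% |
| HbA1c | 5.3, 0.3 | 0.05 to 0.15 | 4-15% |
| Triglycerides | median 110, log-SD 0.4 | CV 10-25% | 13-33% |
| LDL | 110, 28 | 6 to 12 | 27-48% |

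Normal to High is about 0% for glucose, HbA1c and LDL, and 0.3-10% for triglycerides. Impaired or Borderline to High is at most about 0.13% for glucose and 0.5% for HbA1c. It is 31-51% for triglycerides, a cut-off that sustained PCS confirms.

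**5. Second set of assumptions.** Here the SD is total and noise is proportional to level. The any-draw column adds Normal to Borderline/Impaired and Normal to High (for triglycerides at the high CV, 24.9 + 12.7 = 37.6%). The last column requires the worse side of the cut-off at both of the last two draws.

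| Analyte | Mean, total SD, within-subject CV | Any of 5 draws | Last 2 draws |
|---|---|---|---|
| Total cholesterol | 190, 38, 5-8% | 21-32% | 4.7-7.3% |
| LDL | 115, 32, 7-11% | 29-44% | 7.9-13.4% |
| HDL (to Low) | 50, 13, 5-9% | 8-17% | 1.5-2.6% |
| Triglycerides | median 120, log-SD 0.5, 15-25% | 22-38% | 4.3-6.9% |
| Glucose | 93, 10, 4-7% | 22-40% | 4.0-5.8% |
| HbA1c | 5.4, 0.33, 1.5-3% | 11-24% | 2.1-3.6% |

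With one draw instead of five, Normal to Borderline/Impaired is 9-14% for total cholesterol, 9-16% for glucose and 5-9% for HbA1c, so five looks raise it about 2 to 2.6 times. Step to High: 0.9-1.6% for glucose and 0.4-1.2% for HbA1c. Normal to High: 2.8-12.7% for triglycerides and at most 2.4% for the others.

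**6. Denominator.** Under the main LDL assumptions, P(baseline below 100) is Φ(−10/√(28² + 6²)) = 0.36 to Φ(−10/√(28² + 12²)) = 0.37. On all subjects, 27-48% becomes 0.36 × 27 to 0.37 × 48, about 10-18%.

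**7. Two-way comparison.** With no change, baseline and last value are exchangeable, so P(up) = P(down) over all subjects. For glucose (main set, within-subject SD 5) both are 6.6%. About 87.8% start below 100, so by baseline row this becomes 6.6/87.8 = 7.5% worsening and 6.6/12.2 = about 54% improving. The balance shows only on the all-subject denominator.

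**The case against.** Much of this is already handled. Sustained PCS covers these six analytes at the last two assessments. For HbA1c 5.7% it cuts the noise rate from 4-15% to 0.8-2.0% under the main assumptions. Table 3 has change criteria for lipids and fasting glucose, and symmetric noise averages out of the by-visit mean changes. The tables are descriptive, are openly labelled as any postbaseline, and err towards detecting harm. Dropout, including discontinuation at HbA1c of 6.5% or more, means fewer draws and lower rates. Mock tables are in a separate document, so a denominator or footnote may exist there.

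All of this stands, and it limits the point. It does not supply a confirmed level result at total cholesterol 200, LDL 100, triglycerides 150 or glucose 100, nor does it show category movement in both directions.

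A reader might infer that every shift row is inflated by noise, or that the section lacks any confirmation or minimum change. The documents do not support either reading. Five rows carry an implied minimum rise, the diabetes-range rows barely move under noise, and confirmation and change criteria exist in the same section.

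**Conclusion.** The point holds for the adjacent-category rows, and mainly for the four cut-offs without a matching PCS level. If nothing changed, roughly 4-50% of normal-baseline subjects could still be counted as Borderline or Impaired, depending on analyte. That range rests wholly on assumed means, SDs and within-subject variation, on all five draws being taken, and on the baseline category as denominator.

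It does not show that Tables 4 and 5 are wrong or should be dropped, or that an observed worsening would be only noise. The point is about interpretation, and it is cheap to correct with data already planned.

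**What to change.** - Keep Tables 4 and 5 and state their denominator.
- For each parameter, by treatment sequence and overall, add a full two-way shift table from baseline to last on-treatment value. Use percentages of all subjects with a baseline and at least one postbaseline value, so that worsening and improvement cells are directly comparable.
- Extend the existing last-two-assessments rule to the Borderline lipid rows and the Impaired glucose row.
- Footnote that the any-postbaseline rows are not corrected for visit-to-visit variation.

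A net figure (worsened minus improved) is not needed and could hide harm in a subset. The cost is SAP wording and a few more descriptive tables, with no new data.
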